12.4 End of Treatment

Once the EGFRvIII CARS infusion is complete, the treatment phase of the study will be over and the follow-up period will begin.

12.5 Follow-up Period

Following the infusion, blood samples for IM (9 yellow, 1 red) will be drawn 1, 5, 10, and 28 days after the infusion, then 3 and 6 months, then yearly until progression (or death or lost to contact). Lymphocytes in patients' peripheral blood will be analyzed by FACS and quantified for persistence. Isolated PBMCs will be stained with fluorescence-labeled antibodies against cell surface and intracellular cytokine markers to determine function including staining with our novel EGFRvIII tetramer reagent. Whole planar imaging, followed by SPECT/CT, if appropriate, will be done on days 1, 2, and 3 following infusions to determine the IC localization of ¹¹¹In-labeled EGFRvIII CARs. Quantification of radioactivity will be assessed by previously published methods that calculate counts from reconstructed images based on the percentage of injected dose. Blood will be taken for RCR PCR at 3, 6 and 12 months and blood for evaluation of CRS (1 red, 1 purple top – 3mLs each) will be drawn pre-infusion, 1 and 4 hours after CARs infusion, and on days 1, 2, 5, 10, and 28.

Patients treated with EGFRvIII CARs will be followed for survival and data recorded by the study coordinator/research nurse until death or for 15 years (whichever comes first).

12.6 End of Study

Rationale for taking a patient off study will be documented (see section 12.7.1). All patients will be followed for survival, subsequent therapies, and radiographic response and this information will be recorded by the study team.

12.7 Early Withdrawal of Subject(s)

12.7.1 Criteria for Early Withdrawal

Subjects may voluntarily withdraw from the study at any time.

Subjects may be withdrawn by the PI prior to infusion of EGFRvIII CARs for the following:

- Progressive disease following any of the cycles of DI TMZ, at the discretion of the treating physician. *Note that patients who are removed from study due to progressive disease may be eligible for the INTERCEPT study (Pro00083828), this would result in the autologous T cells from the leukapheresis in this study being transferred to the INTERCEPT study (Pro00083828).

The PI may also withdraw a subject from the study at any time based on his/her discretion. Reasons for PI-initiated withdrawal may include, but are not limited to the following:

- Pregnancy.
- Upon request of the subject.
- If, in the investigator's medical judgment, further participation would be injurious to the subject's health or wellbeing.
- Protocol deviation.
- Administrative reasons, such as a major violation of the clinical trial protocol.
- Non-compliance of the subject.

12.7.2 Follow-up Requirements for Early Withdrawal

Subjects who have received EGFRvIII CAR T cell infusion on this study that are withdrawn by the PI for any of the aforementioned reasons will continue to be followed for survival by the study coordinator/research nurse until death or are lost to follow up. This follow-up may include the collection of survival status and doses, dates, and final radiographic responses associated with future treatment regimens.

12.7.3 Replacement of Early Withdrawal(s)

Subjects who do not receive EGFRvIII CAR treatment will be replaced. Subjects who terminate infusion prematurely or are lost to follow-up before the completion of 4 weeks of follow-up observation and do not experience dose-limiting toxicity will also be replaced.

12.8 Study Assessments

12.8.1 Medical History

Medical history will be obtained from the Duke EPIC system and from the subject and/or family at the screening visit and reviewed at **each** study/clinic visit. This data will include the following:

- All past medical and surgical history
- Current medications
- Changes in physical or neurologic symptoms
- Any adverse events

12.8.2 Physical Exam

Vital signs and physical and neurologic examinations will be assessed and recorded along with a KPS score prior to enrollment and at each study/clinic visit.

12.8.3 Correlative Assessments

To assess if EGFRvIII CARs transferred into patients with WHO Grade IV malignant glioma expand and remain functional in the periphery, 2 red top tubes will be drawn at the leukapheresis visit for immune monitoring. Fifty mLs of whole blood in 6 ACD yellow top tubes and 1 red top tube (9 mLs) for immune monitoring will be drawn pre-infusion and 1, 5, 10, and 28 days after CARs treatment, then 3 and 6 months post-infusion, then yearly until progression, death or lost to contact. Patient PBMCs will be obtained from whole blood by purification using centrifugation on a Ficoll cushion within 8 hours of draw using a standard SOP. Cells will be frozen to -70 °C at -1 °C/min and stored in liquid nitrogen. To quantify the kinetics of CARs in blood, the expression of EGFRvIII CARs in PBMCs recovered from patients will be determined using the novel EGFRvIII peptide tetramer reagent developed by our laboratory. The number of CARs will be compared to total numbers of CD4⁺ and CD8⁺ lymphocytes using FACS; Ki67 staining will be used to assess cell proliferation. Cell phenotype and function will be assessed using a validated polyfunctional T cell assay in collaboration with [name]., using the following markers: anchor gates (CD3 AmCyan, CD4 PerCP-Cy5.5 & CD8 APC-Cy7), a multiplexed exclusion channel (CD14 Cascade Blue+ CD19 Cascade Blue+ vAmine all collected in a single channel), maturational markers (CD27 APC, CD57 FITC & CD45RO ECD) to identify naïve (CD45RO-CD27+), central memory (CD45RO+CD27+), effector memory (CD45RO+CD27-), effector (CD45RO+CD57+), and terminal effector (CD45RO-CD57+) CD4⁺ and CD8⁺ lymphocytes, and functional markers (IL-2 PE, TNF-α Alexa700, CD107a PE-Cy5.5 & IFN-γ PE-Cy7). We will include the EGFRvIII peptide tetramer reagent in this assay to evaluate CAR-specific polyfunctionality using a fluorochrome not already in the panel. Samples from the expanded cohort will be analyzed after radioactivity has decayed. Polyfunctional analysis will also be done on the cells transferred to the patients.

Also following infusion of ¹¹¹In-labeled CARs in the expanded cohort, imaging on days 1, 2, and 3 by SPECT/CT will be used to determine the IC localization of ¹¹¹In-labeled EGFRvIII CARs to assess if EGFRvIII CARs traffic to the tumor site. Quantification of radioactivity will be assessed by previously published methods that calculate counts from reconstructed images based on the percentage of injected dose.

For monitoring the RCR PCR assays to detect the GaLV envelop gene, the RCR will be performed using a validated assay prior to cell infusion and at 3 and 6 months, and at one year as required by the FDA. Blood samples will be archived annually thereafter if all previous testing has been negative. If a patient dies or develops neoplasms during this trial, efforts will be made to obtain a biopsy sample for RCR. If any post-treatment samples are positive, further analysis of the RCR and more extensive patient follow-up will be undertaken, in consultation with the FDA.

Please see [Figure 10. Correlative Studies Schemain Appendices](#).

Lastly, blood for evaluation of CRS will be drawn prior to cell infusion, 1 and 4 hours after infusion, and on days 1, 2, 5, 10, and at 28 days. Measurements for CRS include IL-2, IL-6, TNFα, IFNγ, GM-CSF, and CRP.

13 SAFETY MONITORING AND REPORTING

The PI is responsible for the identification and documentation of AEs and SAEs that may occur following treatment with EGFRvIII CARs, as defined below. At each study visit, the PI or designee must assess, through non-suggestive inquiries of the subject or evaluation of study assessments, whether an AE or SAE has occurred. AEs and/or SAEs will be collected starting at the CAR T cell infusion visit and will be recorded for baseline assessments. Only Special Interest AEs related to leukapheresis, as described in [Section 13.2](#) will be recorded prior to the CAR T cell infusion. Following EGFRvIII CAR infusion, all AEs and SAEs will be recorded by the study team (see [Section 13.1.1](#) below).

13.1 Adverse Events

An AE is any untoward medical occurrence in a subject receiving EGFRvIII CARs and which does not necessarily have a causal relationship with this treatment. For this protocol, the definition of AE also includes worsening of any pre-existing medical condition. An AE can therefore be any unfavorable and unintended or worsening sign (including an abnormal laboratory finding), symptom, or disease temporally associated with the use of EGFRvIII CAR T cells, whether or not related to use of the EGFRvIII CAR T cells. All CTCAE-defined AEs, including grade 1 laboratory events, are recorded and reported as required in 21CFR312.

From the time of CAR T cell infusion through the End of Study visit (as defined in Section 12.6), as well as any Special Interest AEs related to leukapheresis (as defined in Section 13.2), all AEs must be recorded in the subject medical record and adverse events case report form. However, for reporting purposes, only AEs that occur at the time of the EGFRvIII CAR T cell infusion or following the infusion will be submitted to the appropriate agencies as indicated.

AEs will be assessed according to the CTCAE version 4.0. If CTCAE grading does not exist for an AE, the severity of the AE will be graded as mild (1), moderate (2), severe (3), life-threatening (4), or fatal (5).

Attribution of AEs will be indicated as follows:

- Definite: The AE is clearly related to the study drug
- Probably: The AE is likely related to the study drug
- Possible: The AE may be related to the study drug
- Unlikely: The AE is doubtfully related to the study drug
- Unrelated: The AE is clearly NOT related to the study drug

13.1.1 Reporting of AEs

A summary of all adverse events (not just those considered related to EGFRvIII CARs) that occur following treatment with EGFRvIII CARs will be kept which will categorize the event by organ system, relationship to treatment, its grade of severity, and resolution. The PI will periodically review the collective adverse events with the intention of identifying any trends or patterns in toxicity. If any such trends are identified, depending on their severity and frequency, a protocol amendment will be considered.

13.2 Adverse Events of Special Interest

Adverse events will not be collected until the patient has received CAR T cells, unless they are considered an Adverse Event of Special Interest related to the leukapheresis procedure. Only these special interest adverse events will be collected prior to CAR T cell infusion, all other events occurring prior to CAR T cell administration will not be recorded or monitored.

Special Interest Adverse Events that may occur during the leukapheresis procedure include:

- Allergic Reaction
- Anaphylaxis
- Presyncope
- Syncope
- Vasovagal reaction

Special Interest Adverse Events that may occur after the procedure, but may still be related to leukapheresis include:

- Vascular Access Complications
- Venous Injury

13.3 Serious Adverse Events

An AE is considered “serious” if in the view of either the investigator or sponsor it leads to one of five specific sequelae:

- Death
- Life-threatening adverse event
- Inpatient hospitalization of 24 hours or longer or prolongation of existing hospitalization
- Persistent or significant incapacity or substantial disruption of the ability to conduct normal life functions
- Constitutes a congenital anomaly or birth defect

Important medical events that may not result in death, be life threatening, or require hospitalization may be considered serious when, based upon appropriate medical judgment, they may jeopardize the patient or subject and may require medical or surgical intervention to prevent one of the outcomes listed in this definition.

13.3.1 Reporting of SAEs

All SAEs that occur following treatment with EGFRvIII CARs should be reported immediately to [name] ([contact]), [name] ([contact]), or their designee [contact]) and to the FDA and Duke University Medical Center IRB. Fatal or life-threatening, unexpected adverse events will be reported to the FDA by telephone, facsimile, or in writing as soon as possible, but no later than 7 calendar days after first knowledge by the sponsor followed by as complete a report as possible within 8 additional calendar days. Serious, unexpected adverse events that are not fatal or life-threatening will be reported to the FDA by telephone, facsimile, or in writing as soon as possible, but no later than 15 calendar days after first knowledge by the sponsor.

All adverse events that are considered serious, unanticipated, and related or possibly related to EGRvIII CARs (as defined by 21CFR312.32[a]) will be reported to the Duke University Medical Center IRB and the FDA using the appropriate SAE report form. At the time of the annual progress report to the Duke University Medical Center IRB and the FDA, a summary of the overall toxicity experience will be provided.

13.4 Safety Oversight Committee (SOCom)

The Duke Cancer Institute SOCom is responsible for annual data and safety monitoring of DUHS sponsor-investigator phase I and II, therapeutic interventional studies that do not have an independent DSMB. The primary focus of the SOCom is review of safety data, toxicities and new information that may affect subject safety or efficacy. Annual safety reviews includes but may not be limited to review of safety data, enrollment status, stopping rules if applicable, accrual, toxicities, reference literature, and interim analyses as provided by the sponsor-investigator. The SOCom in concert with the DCI Monitoring Team (see [Monitoring](#) section for Monitoring Team description) oversees the conduct of DUHS cancer-related, sponsor-investigator therapeutic intervention and prevention intervention studies that do not have an external monitoring plan, ensuring subject safety and that the protocol is conducted, recorded and reported in accordance with the protocol, SOPs, GCP, and applicable regulatory requirements.

14 QUALITY CONTROL AND QUALITY ASSURANCE

14.1 Monitoring

The DCI Monitoring Team will conduct monitoring visits to ensure subject safety and to ensure that the protocol is conducted, recorded, and reported in accordance with the protocol, standard operating procedures, good clinical practice, and applicable regulatory requirements. As specified in the DCI Data and Safety Monitoring Plan, the DCI Monitoring Team will conduct routine monitoring after the third subject is enrolled, followed by annual monitoring of 1 – 3 subjects until the study is closed to enrollment and subjects are no longer receiving study interventions that are more than minimal risk.

Additional monitoring may be prompted by findings from monitoring visits, unexpected frequency of serious and/or unexpected toxicities, or other concerns and may be initiated upon request of DUHS

and DCI leadership, the DCI Cancer Protocol Committee, the SOCom, the sponsor, the Principal Investigator, or the IRB. All study documents must be made available upon request to the DCI Monitoring Team and other authorized regulatory authorities, including but not limited to the National Institute of Health, National Cancer Institute, and the FDA. Every reasonable effort will be made to maintain confidentiality during study monitoring.

14.2 Audits

The Duke School of Medicine OARC office may conduct audits to evaluate compliance with the protocol and the principles of GCP. The PI agrees to allow the OARC auditor(s) direct access to all relevant documents and to allocate his/her time and the time of the study team to the OARC auditor(s) in order to discuss findings and any relevant issues.

OARC audits are designed to protect the rights and well-being of human research subjects. OARC audits may be routine or directed (for cause). Routine audits are selected based upon risk metrics generally geared towards high subject enrollment, studies with limited oversight or monitoring, Investigator initiated Investigational Drugs or Devices, federally-funded studies, high degree of risk (based upon adverse events, type of study, or vulnerable populations), Phase I studies, or studies that involve Medicare populations. Directed audits occur at the directive of the IRB or an authorized Institutional Official.

OARC audits examine research studies/clinical trials methodology, processes and systems to assess whether the research is conducted according to the protocol approved by the DUHS IRB. The primary purpose of the audit/review is to verify that the standards for safety of human subjects in clinical trials and the quality of data produced by the clinical trial research are met. The audit/review will serve as a quality assurance measure, internal to the institution. Additional goals of such audits are to detect both random and systemic errors occurring during the conduct of clinical research and to emphasize “best practices” in the research/clinical trials environment.

14.3 Data Management and Processing

14.3.1 Study Documentation

Study documentation includes but is not limited to source documents, case report forms, monitoring logs, appointment schedules, study team correspondence with sponsors or regulatory bodies/committees, and regulatory documents that can be found in the DCI-mandated “Regulatory Binder”, which includes but is not limited to signed protocol and amendments, approved and signed informed consent forms, FDA Form 1572, CAP and CLIA laboratory certifications, and clinical supplies receipts and distribution records.

Source documents are original records that contain source data, which is all information in original records of clinical findings, observations, or other activities in a clinical trial necessary for the reconstruction and evaluation of the trial. Source documents include but are not limited to hospital records, clinical and office charts, laboratory notes, memoranda, subjects’ diaries or evaluation checklists, pharmacy dispensing records, recorded data from automated instruments, copies or transcriptions certified after verification as being accurate copies, microfiches, photographic negatives, microfilm or magnetic media, x-rays, subject files, and records kept at the pharmacy, at the laboratories and at medico-technical departments involved in the clinical trial. When possible, the original record should be retained as the source document. However, a photocopy is acceptable provided that it is a clear, legible, and an exact duplication of the original document.

14.3.2 Case Report Forms (CRFs)

The subject’s medical records and CRFs will be the primary source document for the study. This data will be transferred to the electronic database. Only the PI, key personnel, the Radiolabeled Pharmacy personnel, and the PRTBTC data manager are permitted to make entries, changes, or corrections in the source documents or database.

Errors on the source documents will be crossed out with a single line, and this line will not obscure the original entry. Changes or corrections will be dated, initialed, and explained (if necessary). Electronic database changes will be tracked automatically. The PI or authorized key personnel will maintain a record of the changes and corrections.

For electronic CRFs, an audit trail will be maintained by the electronic CRF management system.

14.3.3 Data Management Procedures and Data Verification

The DCI IS Shared Resource has a track record of developing Title 21 CFR Part 11 compliant databases for cancer clinical trials. IS also has extensive expertise in database quality assurance, data standards, and use of caBIG tools to support cancer researchers.

Data queries will be generated automatically by the eCRF system. These data queries signify the presence of data inconsistencies. The study and data management team will cross-reference the data to verify accuracy. Missing or implausible data will be highlighted for the PI requiring appropriate responses (i.e., confirmation of data, correction of data, completion or confirmation that data is not available, etc.).

The database will be reviewed and discussed prior to database closure, and will be closed only after resolution of all remaining queries. An audit trail will be kept of all subsequent changes to the data.

14.3.4 Coding

All medical terms will be coded using CTCAE (version 4).

14.3.5 Study Closure

Following completion of the studies, the PI will be responsible for ensuring the following activities:

- Data clarification and/or resolution
- Accounting, reconciliation, and destruction/return of used and unused study drugs
- Review of site study records for completeness
- Shipment of all remaining laboratory samples to the designated laboratories

15 STATISTICAL METHODS AND DATA ANALYSIS

All statistical analysis will be performed under the direction of the statistician designated in key personnel. Any data analysis carried out independently by the investigator must be approved by the statistician before publication or presentation.

15.1 Analysis Sets

EGFRvIII CAR Efficacy Analysis Set: Efficacy analyses will focus on two groups of patients: all patients, and the subgroup of patients who receive EGFRvIII CAR.

Overall EGFRvIII CAR Safety Analysis Set: For monitoring purposes and for reporting to appropriate agencies, safety analyses will include all patients who receive any EGFRvIII CAR treatment.

MTD Analysis Set: For the determination of MTD, patients without DLT who do not complete 4 weeks of follow-up after CAR infusion or do not complete the intended infusion will be excluded from the Overall EGFRvIII CAR Safety Analysis Set to create the MTD Analysis Set.

15.2 Patient Demographics and Other Baseline Characteristics

Patient clinical and socio-demographic characteristics will be summarized for all patients enrolled on this study, as well as the subgroup of patients who receive EGFRvIII CAR treatment. Categorical descriptors will be summarized using frequency distributions; whereas, interval variables will be summarized using percentiles, as well as means and standard deviations.

15.3 Treatments

The number of patients who receive EGFRvIII CAR treatment will be summarized by dose level.

15.4 Primary Objective

Within this “3+3” phase I study, the primary objective is to determine the MTD of a single IV infusion of EGFRvIII CAR T cells in patients with newly-diagnosed WHO grade IV malignant glioma. Four dose levels will be considered based on transduced cells/kg: #1: 4.5×10^6 /kg, #2: 1.5×10^7 /kg, #3: 4.5×10^7 /kg, and #4: 1.5×10^8 /kg. The MTD is the highest dose level at which ≤ 1 or 6 patients experience dose-limiting toxicity during the 4 weeks after CAR infusion. Section 9.1.2 provides information about what constitutes a dose-limiting toxicity. Section 9.1.1 provides details concerning the determination of the MTD.

15.5 Secondary Objectives

To determine the DLT of a single IV infusion EGFRvIII CAR T cells in patients with newly-diagnosed WHO grade IV malignant glioma. The proportion of patients who experience DLT within each dose level will be tabulated.

15.6 Exploratory Objectives

1. To determine if CARs transferred into patients with WHO grade IV malignant glioma being treated with TMZ expand.
2. To determine if EGFRvIII CARs persist and remain functional in the periphery.
3. To assess whether EGFRvIII CARs traffic to the site of EGFRvIII expressing WHO grade IV malignant glioma.
4. To describe the survival experience of patients with newly diagnosed, EGFRvIII-expressing WHO grade IV malignant glioma treated with EGFRvIII CAR T cells.
5. To describe the progression free survival experience of EGFRvIII-expressing newly-diagnosed WHO grade IV malignant glioma patients treated with EGFRvIII CAR T cells.

The analyses that address the exploratory correlative study objectives will be exploratory and descriptive. Based upon PBMCs collected from the peripheral blood, the median number of EGFRvIII CARs, the median percentage of CD4⁺ and CD8⁺ lymphocytes that are CARs, and the median level of Ki67 will be estimated at each assessment time. Assuming laboratory analyses demonstrate

CARs are present in the periphery, functional analyses may be conducted focusing on specific functions or time points. Generalized linear models may be used to explore how these phenotypes change over time as a function of dose.

Among patients within the expansion cohort who have been treated with ¹¹¹In-labeled EGFRvIII CARs, the median proportion of injected ¹¹¹In-labeled EGFRvIII CARs present in tumors will be estimated at each assessment point. If the planar image provides no signal and the SPECT/CT is not conducted, we will impute the number of ¹¹¹In-labeled EGFRvIII CARs present in tumors as 0.

Two sets of efficacy analyses will be conducted. One set of analysis will focus on all patients who enroll in the study whether or not EGFRvIII CAR treatment is administered, and the other set of analyses will focus on patients who receive EGFRvIII CAR treatment. Among all patients, Kaplan-Meier methods will graphically describe their survival from the time of study enrollment or histologic diagnosis. Among patients who receive CAR treatment, Kaplan-Meier methods will also be used to describe the distribution of overall survival and progression-free survival. In these analyses, OS and PFS will be computed from the date that CAR treatment was initiated. OS is defined as the time between the landmark (e.g. histologic diagnosis or initiation of CAR treatment) and death or date of last follow-up. PFS is defined as the time between the landmark and first progression, death, or last follow-up if the patient remains alive without disease progression.

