9 INVESTIGATIONAL PLAN

9.1 Study Design

Treatment Plan

Following consent, subjects who are part of the dose escalation cohort will be assigned into the appropriate dose-escalation cohorts. Patients will undergo a 2-4 hour leukapheresis to harvest PBMCs for the generation of EGFRvIII CAR T cells prior to beginning RT and concurrent TMZ. T cells will be isolated from the patient's PBMCs and transduced to express CARs. Briefly, PBMC will be stimulated with OKT3 (anti-CD3 mAb) and transduced on RetroNectin® coated plates. Transduced cells will be expanded in IL-2 for 14 days.

Patients will then complete approximately 6 weeks of standard of care RT and concurrent TMZ at a targeted dose of 75 mg/m²/d. Patients whose blood counts do not meet eligibility within 6 weeks of completing standard of care RT and concurrent TMZ will be withdrawn from the study before initiation of TMZ treatment and replaced. Patients who appear to have progressive disease following radiation may actually have pseudoprogression due to the radiation and will be allowed to continue to cycle 1 of (dose intensified) DI TMZ in order to not be excluded from the study prematurely, at the discretion of the treating physician. If the patient is determined to have progressive disease, the patient may be eligible for the INTERCEPT study (INTRacerebral EGFR-vIII Chimeric Antigen Receptor Gene-Modified T Cells for PaTients with Recurrent GBM, Pro00083828). If the patient is determined to be eligible for the INTERCEPT study (Pro00083828), the cells extracted from leukapheresis while they were on this study, ExCeL, will be used to create the CAR T cells for administration in the INTERCEPT study.

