9.4 Definition of Evaluable Subjects, On Study, and End of Study

While all patients who received any EGFRvIII CAR T cells will be included in safety summaries for the purposes of monitoring and reporting of adverse events to appropriate agencies, patients evaluable for determination of the MTD will include:

- Patients who receive the entire CARs infusion (i.e. the infusion is not stopped prematurely), and 2) have 4 weeks of follow-up for adverse events after the infusion
- Patients who receive the entire CARS infusion (i.e. the infusion is not stopped prematurely) and terminated follow-up prematurely during the 4 week follow-up period after having experienced a DLT.
- Patients who terminate infusion before completion due to a DLT

For the efficacy analyses, evaluable patients will include two groups of patients: all patients, and the subgroup of patients who receive EGFRvIII CAR. Once a patient's eligibility is confirmed after completion of XRT/TMZ, that subject will be considered "on study". The rationale for taking a patient off study will be documented. Please see Section 12.7 for information on patient withdrawals.

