12 SCREENING AND ON-STUDY TESTS AND PROCEDURES

In brief, patients will be screened and evaluated for study entry (please see [Table 6](#)). The screening examination must include a pathology report confirming the EGFRvIII+ WHO grade IV malignant glioma diagnosis. Blood tests per [Table 6](#) will be drawn as well as the post-surgical MRI. The baseline physical and neurologic examination with KPS score will be performed and documented by the neuro-oncology team and verified by the study team during the Duke Brain Tumor Center clinic visit (of note, the standard of care clinic visit may be used to fulfill the initial screening visit requirement). Patients will be offered treatment options during this BTC clinic visit.

Once the consent has been signed, patients will be scheduled to undergo a leukapheresis in order to obtain T cells for infusion (please see [Table 6](#)). Patients will then receive approximately 6 weeks of standard of care RT and concurrent TMZ at a standard targeted dose of 75 mg/m²/d. Patients whose blood counts do not meet eligibility within 6 weeks of completing standard of care RT and concurrent TMZ will be considered a screen failure. Patients who appear to have progressive disease following radiation may actually have pseudoprogression due to the radiation and will be allowed to continue to cycle 1 of DI TMZ in order to not be excluded from the study prematurely, at the discretion of the treating physician. If the patient is determined to have progressive disease, the patient may be eligible for the INTERCEPT study (INTracerebral EGFR-vIII Chimeric Antigen Receptor Gene-Modified T Cells for PaTients with Recurrent GBM, Pro00083828). If the patient is determined to be eligible for the INTERCEPT study (Pro00083828), the cells extracted from leukapheresis while they were on this study, ExCeL, will be used to create the CAR T cells for administration in the INTERCEPT study.

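### All-patient survival may be counted from diagnosis by plain Kaplan-Meier while enrollment is never tied to an event, which builds in guaranteed survival time of unclear length

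*Combined protocol and SAP*

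**What the plan says.** **Who is in the set.** Section 15.1: "Efficacy analyses will focus on two groups of patients: all patients, and the subgroup of patients who receive EGFRvIII CAR". Section 9.4 describes the same two groups, and Section 15.6 adds: "One set of analysis will focus on all patients who enroll in the study whether or not EGFRvIII CAR treatment is administered".

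**Time origin.** For the first group, Section 15.6 says: "Among all patients, Kaplan-Meier methods will graphically describe their survival from the time of study enrollment or histologic diagnosis". Its definition of overall survival refers to a landmark and offers diagnosis and start of CAR treatment only as examples. For CAR-treated patients, survival and progression-free survival start at CAR treatment.

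**When a patient enters.** Section 9.1 places cohort assignment straight after consent: "Following consent, subjects who are part of the dose escalation cohort will be assigned into the appropriate dose-escalation cohorts". Section 12.2 also speaks of patients as having consented onto the study before leukapheresis. Section 9.4, however, says that once a patient's "eligibility is confirmed after completion of XRT/TMZ, that subject will be considered" on study. Section 12.1 calls the visit after radiation the final screening visit and uses its blood results to settle eligibility.

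**Blood-count failures after RT.** In Section 9.1 they are "withdrawn from the study before initiation of TMZ treatment and replaced". In Section 12 the same patients "will be considered a screen failure", and Section 12.1 agrees with Section 12.

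**Survival follow-up.** Section 12.6 covers all patients. Sections 12.5 and 12.7.2 name only patients who received CAR T cells.

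**The concern.** A patient can be counted only if alive at entry. If the clock starts at diagnosis and entry comes later, the interval between them contains no deaths by construction. Plain Kaplan-Meier treats the patient as at risk throughout that interval and so overstates survival. The remedy is to start the clock at entry, or to admit each patient to the risk set only from entry (left truncation). Section 15.6 does neither for the diagnosis option.

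The length of the interval depends on what enrollment means, which the plan does not say. The meaning also decides whether patients who do badly during or just after RT are in the curve. The choice of origin and denominator could therefore be made after the data are seen.

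This curve is the only planned survival analysis that does not select on reaching infusion. Any reader who sets it beside the 14.6-month median quoted in Section 7.1.1 would be comparing it with a figure that carries no such guaranteed time by design of this trial. The baseline summary in Section 15.2, for all patients enrolled, has the same unclear denominator.

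**Working it through.** The plan states no survival target, event count or power, so there is no figure of its own to reproduce. The check compares the possible readings and sizes each one.

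**Inputs**
- Median survival 14.6 months (Section 7.1.1), for illustration only.
- RT with TMZ: about 6 weeks (Sections 9.1 and 12).
- Recovery of counts: up to 6 weeks after RT (Sections 9.1, 12 and 12.1).
- Diagnosis to consent: not given; assumed 0 to 5 weeks.
- Diagnosis to start of RT: not given. Taken as zero for a lower bound, then assumed 2 to 6 weeks.
- 1 week = 7/30.4375 = 0.230 months.

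**Formula.** With entry at time L after diagnosis, the curve estimated from diagnosis is S(t)/S(L), so the apparent median M solves S(M) = 0.5 × S(L).
- Exponential: M = 14.6 + L.
- Weibull, shape 1.5 (rising hazard): M = (14.6^1.5 + L^1.5)^(2/3).
- Share of deaths falling before entry: 1 − S(L).

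**Results with diagnosis as origin**

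| Entry event | L (weeks) | L (months) | Exponential median | Deaths before entry | Weibull 1.5 median | Deaths before entry |
|---|---|---|---|---|---|---|
| Consent | 0 to 5 | 0 to 1.15 | 14.6 to 15.75 | 0 to 5.3% | 14.6 to 14.8 | 0 to 1.5% |
| On study, RT and counts only | 6 to 12 | 1.4 to 2.8 | 16.0 to 17.4 | 6.3 to 12.3% | 14.9 to 15.4 | 2.0 to 5.5% |
| On study, plus assumed 2 to 6 weeks from diagnosis to RT | 8 to 18 | 1.8 to 4.1 | 16.4 to 18.7 | 8.4 to 17.8% | 15.0 to 16.0 | 3.1 to 9.9% |

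Worked line (12 weeks): 12 × 0.230 = 2.76 months. Exponential: 14.6 + 2.76 = 17.4. Weibull: 14.6^1.5 = 55.79 and 2.76^1.5 = 4.58; their sum is 60.37, and 60.37^(2/3) = 15.4.

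**With enrollment as origin.** Guaranteed time is zero under either meaning of enrollment. If enrollment means on study, though, patients lost before that point are still absent, so the curve describes a selected group.

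**Count failures.** In Section 9.1 they are withdrawn, which implies that they had entered; in Sections 12 and 12.1 they are screen failures, which ordinarily implies that they had not. No section says which status governs the all-patient set.

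**The case against.** Much of the case on the other side stands.

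- A reader might infer that the all-patient set is itself defined inconsistently, or that screen failures are excluded from it. The documents do not support this. Sections 9.4, 15.1 and 15.6 word the set alike, and no section removes screen failures. The on-study sentence in Section 9.4 follows the definition of the set but is not linked to it. The fault is an undefined entry event and two labels for the same patients.
- A reader might take a 10% to 19% inflation of the median (16.0/14.6 to 17.4/14.6) as the expected size. It needs three conditions together: entry after RT, diagnosis as origin, and an exponential curve. With consent as entry the shift is about 0 to 1 month; with enrollment as origin there is no guaranteed time.
- The survival objective concerns patients treated with CAR T cells, and that analysis starts at CAR treatment. A reader might suppose that it carries the same bias; it does not.
- The curve is exploratory and descriptive. No test, decision rule or comparison with 14.6 months is planned. Numbers are small: at most 4 × 6 = 24 escalation plus 12 expansion patients are planned for treatment. With 36 deaths and an exponential median of 14.6 months, an approximate 95% interval is 14.6 × exp(±1.96/√36) = 10.5 to 20.2 months, wider than any shift in the table.

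These points limit the importance, not the fault. Imprecision does not excuse a bias with a known direction, and the diagnosis option as written has one under any entry later than diagnosis.

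**Conclusion.** The concern holds in limited form and is minor. Section 15.6 allows a diagnosis origin with plain Kaplan-Meier and no delayed entry, enrollment is not tied to an event, and count failures after RT carry two incompatible labels.

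The bias is upward. Guaranteed time is about 0 to 1 month if entry is consent, which rests on an assumed gap of 0 to 5 weeks. It is at least 1.4 to 2.8 months if entry is on study, because the interval from diagnosis to RT comes on top. In the on-study case a 14.6-month median would appear as about 16.0 to 17.4 months under an exponential curve, or 14.9 to 15.4 under a Weibull curve of shape 1.5. Only on that reading are early failures also left out; the documents do not say that they are.

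**What to change.** 1. Define enrollment as signed consent, and use that date as the single origin for the all-patient curve.
2. State that patients who later fail counts, are withdrawn or are replaced stay in the all-patient set. Say also that anyone who consents but fails the laboratory tests before leukapheresis is included, so that the denominator is explicit.
3. Use one term for count failures after RT in Sections 9.1, 12 and 12.1.
4. If a curve from diagnosis is also wanted, use left-truncated Kaplan-Meier with entry at consent.
5. Align Sections 12.5 and 12.7.2 with Section 12.6, so that patients who never receive CAR T cells are followed for survival. Without this, the all-patient curve may not be estimable.

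The cost is mainly wording, plus survival follow-up of untreated patients, which Section 12.6 already promises. The reported median may be slightly shorter. A left-truncated curve may be unstable early on, when few patients are at risk, so the numbers at risk should be shown with it.
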